E. Prospective Study: All sites will begin recruiting patients by the beginning of study Month 13. As most cancer programs have at least rudimentary patient tracking and navigation, this degree of usual care will serve as the control. All providers will receive the co-morbid illness educational checklist at all sites and will receive monthly data concerning surgical rates by comorbid condition and race. Patients will be randomized to either usual care or a more intense communication intervention delivered by a trained cancer communication educator as described below. Since we are building on the methods of our prior cohort study, pretesting of recruitment methods and study instruments can proceed quickly before randomization. Lung cancer surgery rates in the control groups will be compared to historical controls at the individual sites to account for a passive effect of the registry and educational checklist. As care registries and data compilation by race is a mandate of the HITECH portion of the American Recovery and Reinvestment Act, we don't believe that it's ethical to deny any group access to the registry. Given the flat rate of lung cancer surgery and persisting racial gap documented for over a decade in datasets of national scope [7, 36, 38], historical controls for this portion of the study are justified.

1. Inclusion and Exclusion Criteria for Patients

We will enroll patients who meet these criteria: (1) age 21 years or greater; (2) a probability of 60% or higher of a lung lesion being malignant as calculated by Bayesian analysis derived from clinical and radiographic criteria or, alternatively, biopsy proven disease; and (3) the patient has received a clinical classification of stage I or II disease. By "clinically classified", we mean using all studies including CT scans, PET scans, bone scans, mediastinoscopy, and / or any study or procedure performed short of thoracotomy.

We will exclude patients from this study for 3 reasons: (1) incarceration / ward of the state status, (2) severe cognitive impairment, (3) absolute contraindications by pulmonary function testing, or (4) Non-English speaking. Hispanic patients represent less than 4 percent of lung cancer patients in North Carolina restricting our ability to document an intervention effect.

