Patient flow from the time of initial diagnostic studies, to actual diagnosis and to treatment differs at every site. We are experienced with these patterns and can incorporate recruitment strategies into the clinical flow of care. The UNC patients are all processed through a central site, the Multi-disciplinary Thoracic Oncology Program (MTOP). Note that a patient list is available the Friday prior to MTOP clinic. This list includes patients' names, the description of his or her lung lesion, diagnosis, cancer stage (if determined), and whether the appointment is an initial appointment or follow-up visit. The RA and site PI will identify patients, in advance, who are most likely to be study candidates. The appropriate clinicians will be approached at the beginning of MTOP to confirm the patient's study eligibility and to obtain permission to approach the patient. As MTOP only meets one day a week and in a single location, a research assistant will spend every Tuesday at the MTOP site and work with staff to identify specific patients that meet inclusion criteria, obtain informed consent, and arrange a time for completion of the patient questionnaire. The RA will administer all questionnaires orally, and all participating patients will be paid \$30 at completion. Patients will also receive \$10 for each completed follow-up interview (6 months then 12 months after enrollment). At ECU, the format is identical except about one-fifth of lung cancer patients enter the system through a standard pulmonary clinic. The review of the patient list, the confirmation of eligibility, and enrollment process at ECU will proceed exactly as per the description at UNC. Lung cancer care in Greensboro has been decentralized in the past. However, the regional cancer center has recruited a lung cancer navigator and established a formal MTOP structure. All lung cancer providers (thoracic surgeons, pulmonologists, oncologists, and radiation oncologists) have agreed to refer potential and diagnosed lung cancer patients for case discussion to the program clinic prior to surgical or other treatment decisions and will utilize a multidisciplinary and multi-specialty decision-making format. Patients will now be accessible at a common site before treatment decisions are finalized. The MTOP clinic roster will be available to the RA and site PI 48 hours in advance and the patient identification and enrollment process will proceed as described at ECU and UNC.

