USC also has an MTOP conference but about one-third of patients are discussed after therapy has been determined by the referring physician. However, the pulmonary division has established a solitary pulmonary nodule clinic specifically designed to identify patients with early stage lung cancer who then rapidly progress to diagnostic evaluation and treatment recommendations. There are 2 clinic sessions per month and 15 patients evaluated in each clinic. The USC site investigator and RA will have access to the nodule clinic schedule and determine potential patient eligibility prior to clinic. As with the MTOP clinics above, the RA will attend the nodule clinic, the appropriate clinicians will be approached to confirm patient's study eligibility and to obtain permission to approach the patient. We will also intensify recruitment at thoracic surgery offices in an effort to capture the patients treated prior to MTOP and not seen in solitary nodule clinic. Note that none of the participating sites use formal communication protocols that define minimum information delivery or ascertainment of patient comprehension.

All 4 study sites are referral centers for lung cancer treatment with large catchment areas. We surveyed the lung cancer physicians and coordinators at all 4 centers regarding a potential diffusion effect between study patients and controls. Because of widespread geographic distribution of patients and MTOP scheduling sequences during visits the possibility of intervention and control patients meeting and discussing variations in communication is remote. To further ensure against a diffusion effect, we will alternate control and intervention recruitment dates as part of the randomization scheme.

In our cohort study, 80% of the patients enrolled identified a pulmonologist, thoracic surgeon, or oncologist as the individual who told them the most about lung cancer. These specialists

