
B. Data Feedback – Results of the retrospective chart review will be distributed to and reviewed with all lung cancer care providers at their participating institutions. Particular emphasis will be placed on the role of co-morbid conditions and outcomes according to race (VII). Since small clusters of physicians perform nearly all lung cancer care in each health system, cross-contamination for any physician-specific intervention is very likely. Therefore, prospective physician feedback will be delivered at all institutional sites. Cumulative data feedback that includes race, co-morbidity variables and surgical rates will be presented to lung cancer providers *by an identified physician champion at each clinical site* quarterly. “Drop outs” and negative provider recommendations will be flagged in real time. The clinic champion will arrange intensive clinical review if the barrier stems from clinical recommendations while the CCE will re-examine patient related barriers. Current IT systems at cancer care organizations do not often factor in patient race, track “real time” clinical performance, generate regular provider reports or suggest options for improvement (V). Although routine quality improvement has not always been effective in addressing disparities [28], we will create a race-specific registry for our study patients similar to the effective registry that Bickell et al. [16] employed for adjuvant breast cancer therapies. We will follow the effect of the registry function via historical controls.

- C. Registry development – note that [name] and [name] have past experience designing a diabetes registry with care flags and point of care reminders that is utilized for paper-based practices in a statewide quality improvement project (formally IPIP, now the North Carolina Healthcare Quality Alliance). The same electronic backbone will be used to track appointments, procedures, adherence and recommendations related to care for early stage, non-small cell, lung cancer.

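### Arm is tied to alternating recruitment dates with no concealment described, which exposes the only randomised comparison to selection bias

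*Protocol*

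**What the plan says.** Protocol section E (Prospective Study) states: "Patients will be randomized to either usual care or a more intense communication intervention". How this is done appears once, at the end of the diffusion discussion in section E.2 (Patient Recruitment). There the stated purpose is "To further ensure against a diffusion effect", and the method is that "we will alternate control and intervention recruitment dates as part of the randomization scheme". The sentence before it says that "the possibility of intervention and control patients meeting and discussing variations in communication is remote". The SAP adds nothing on allocation. Neither document describes how the sequence is generated, whether the order of dates is random, who knows it, or when a patient's arm is revealed.

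The same section describes what staff know before the recruitment date:

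- **UNC, and ECU by the same format:** "Note that a patient list is available the Friday prior to MTOP clinic". The list shows lesion, diagnosis, stage where determined, and visit type. "The RA and site PI will identify patients, in advance, who are most likely to be study candidates".
- **Greensboro:** "The MTOP clinic roster will be available to the RA and site PI 48 hours in advance".
- **USC:** the site investigator and RA screen the nodule clinic schedule before each session.
- **In these clinics:** a clinician confirms eligibility and gives permission for the approach.
- **Office referrals:** staff telephone the patient and arrange the consent meeting.

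Registry, feedback and checklist reach every site and are not randomised; for the registry, section E.4.B says "We will follow the effect of the registry function via historical controls".

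**The concern.** Strict alternation is deterministic: anyone who knows one date's arm knows the next. The people who decide whom to approach, and sometimes when, hold both the calendar and the names beforehand. They can also partly anticipate the outcome. Section E.1 describes patients who tend to refuse surgery without a certain diagnosis, and section E.2 describes a group likely to resist it. No bad faith is needed. A recruiter or clinician may simply be less ready to put a reluctant patient forward on one kind of day than on the other.

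Hypothesis 1a rests on this contrast. If willingness to have surgery differs between arms at enrolment, the difference in surgery rates mixes the communicator's effect with selection. Willingness is largely unmeasured, and an intention-to-treat analysis does not help, because the selection happens before enrolment.

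**Working it through.** **Inputs.** From SAP section 7: 496 patients, reference surgery rate 0.63, target 0.69, 80% power. From SAP section 6: two-sided alpha 0.05. Assumed, because no ratio is stated: 1:1 allocation, so 496/2 = 248 per arm.

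**1. The plan's own figure.** One-sample test of a proportion:

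- Null SE = √(0.63×0.37/496) = 0.0217. Alternative SE = √(0.69×0.31/496) = 0.0208.
- Power = Φ[(0.06 − 1.96×0.0217)/0.0208] = 80.0%.

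The figure reproduces. It compares all 496 patients with the previous study, so it says nothing about the two arms.

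**2. Detectable difference for the randomised contrast.** Two-sample test, 248 per arm, with a pooled SE under the null and an unpooled SE under the alternative:

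- 0.63 versus 0.69 has 29.1% power; 80% would need 978 per arm.
- The difference detectable with 80% power is 0.63 versus about 0.746, or 11.6 points.

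**3. Differential enrolment.** Assume no true effect, a control arm at 0.63, and both arms filled to 248. If a fraction x of patients who would not have surgery goes unenrolled on intervention dates, the intervention rate is 0.63/[0.63 + 0.37(1 − x)].

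| x | Calculation | Intervention rate | False difference | Two-sided 5% test rejects |
|---|---|---|---|---|
| 10% | 0.63/0.963 | 0.654 | 2.4 points | 8.7% |
| 20% | 0.63/0.926 | 0.680 | 5.0 points | 21.8% |
| 30% | 0.63/0.889 | 0.709 | 7.9 points | 46.1% |

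The documents give no value for x. The table is a range, not an estimate.

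**4. Swapping patients between dates.** Suppose k surgery-prone patients move to intervention dates and k surgery-averse patients move to control dates. If the two groups' surgery rates differ by d, the false difference is 2kd/248.

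- Perfect prediction (d = 1): k = 5 gives 10/248 = 4.0 points; k = 10 gives 8.1.
- Assumed rates of 0.80 and 0.40 (d = 0.4): k = 5 gives 4/248 = 1.6 points; k = 10 gives 3.2.

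**5. Predictability.** Simulated over 496 allocations, with the guesser aware of earlier ones, the share guessed correctly was about 100% for strict alternation, 68% for random blocks of 4, 6 or 8, and 50% for simple randomisation.

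**6. Clustering by date.** Section E.2 gives UNC a weekly clinic, ECU the same format, and USC two sessions a month. If Greensboro is also weekly (an assumption), that is 52 + 52 + 52 + 24 = 180 dates a year. Section E.2 expects 165 patients a year, so 165/180 ≈ 0.9 per date, and fewer once office and CT-identified recruits are set aside. SAP section 7 reports previous-study correlations of at most 0.01, though not measured by date. The design effect is then close to 1.

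**The case against.** Several points on the other side carry weight.

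- **The scheme is only partly described.** Alternation is called part of the randomisation scheme. A reader might infer that every allocation was known in advance. The documents do not establish that: the order of dates could be random or withheld by a step that is not written down. But neither document mentions such a step, and even with a random order, once a date's arm is known every later patient that day shares it.
- **Discretion is limited.** Section E.1 includes biopsy-proven stage I or II patients automatically. The advance list does not show willingness to have surgery, and the interval between diagnosis and treatment restricts deferral. This narrows the opening without closing it. Patients without tissue enter on a calculated malignancy probability, clinicians must still permit the approach, and office patients' meeting dates are set by staff.
- **The analysis adjusts.** SAP section 6 forces comorbid illness and selected baseline scores into the model. That helps with measured imbalance, not with unmeasured willingness.
- **Alternation has a purpose.** It guards against diffusion, and the protocol's reassurance on diffusion rests partly on how clinic visits are scheduled, so mixing arms on one day is not wholly free. Still, the protocol rates the risk as remote.

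A reader might also infer that date clustering invalidates the patient-level analysis, or that USC has exactly one session per arm each month. Step 6 makes the first unlikely to matter. The second does not follow, since USC also recruits through thoracic surgery offices and how dates apply there is unstated.

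**Conclusion.** The concern stands as one of exposure. As written, arm follows the calendar and no concealment is described, so hypothesis 1a depends on recruiters and clinicians not acting, even unconsciously, on an arm they can predict. A reader might go further and conclude that the comparison was biased. The documents show neither that selection occurred nor in which direction.

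The size depends on assumptions the documents cannot settle. With 248 per arm, a base rate of 0.63 and no true effect, 10% to 20% differential non-enrolment of reluctant patients produces a false 2.4 to 5.0 points. Swapping five patients each way produces 1.6 to 4.0 points, depending on how well surgery can be predicted. It is tempting to set these against the plan's 6 points as the detectable effect, but that figure comes from the one-sample historical comparison. Against the 11.6 points detectable in the randomised contrast they are smaller in proportion (5.0/11.6 = 0.43), yet large enough to raise the false-positive rate well above 5%.

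**What to change.** Replace date alternation with individual allocation, made after eligibility is confirmed and consent given, from a concealed central list in random-size blocks stratified at least by site. Stratifying by race as well is optional. Time it so that the first communicator session, which section E.4.A places at initial diagnosis, is not delayed; the baseline questionnaire may be arranged separately, so the protocol should state the order of these steps.

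If date blocks must stay, randomise the date order within site and conceal it from recruiters and clinicians until after consent as far as possible. Log all eligible patients by date, enrolled or not, so that differential enrolment can be examined, and check clustering by date in a sensitivity analysis.

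The cost is protocol wording and a central allocation list, with the sample size unchanged at 496. Random-size blocks do not remove guessing entirely (about 68% in step 5 when past allocations are known), but they are far less predictable than alternation. The remaining downside is that patients from both arms may attend on the same day.

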C. Early Stage, Non-Small Cell, Lung Cancer Cases: The table below includes number of patients from 2007 with stage I and II, non-small cell lung cancer entered in each local cancer registry. These data only include patients with tissue proven diagnoses and not those who had CT lesions with extremely high cancer probability and refused surgery or dropped out of follow-up (we did include these patients in our prospective study). Therefore, eligible patients are underestimated while "percent surgery" rates are overestimated when factoring in all patients with early stage, non-small cell disease.

Site	Number of Cases	African-Americans	Percent Surgery
ECU	63	11	70
MCHS	141	24	69
UNC	57	14	74
USC	66	17	75

From our prospective study, we anticipate an average recruitment rate of 70% across sites. Only 11% of all patients approached during the post-diagnosis – pre-treatment recruiting interval refused participation and there was no difference by race.

D. Retrospective Chart Review: Our recently completed study demonstrated that co-morbid

conditions differentially affected black patients' care. Given these data, during the first six months of the intervention trial we will perform a retrospective chart review for the 2008 and 2009 calendar years. We will review all patients diagnosed with stage I or II, non-small cell cancer to serve as a baseline for surgical rates and to examine outcomes of patients treated with and without surgery using a very specific analysis of co-morbid conditions and severity. These data will be checked against Strand's report [45] to assess compatibility and level of detail. The results will be used by our expert panel of co-investigators and site investigators to create an educational checklist to remind lung cancer providers that surgical contra-indications are often relative and subjective. We anticipate the availability of approximately 100-150 charts per site in the 2-year pre-study window. Charts will be selected using appropriate ICD-9 billing codes. Data will be collected in an aggregate manner and no linkage files or specific patient identifiers will be maintained.

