almost uniformly will refer their patients to an MTOP. However, the remaining 20% whose CT scans are suggestive of early stage lung cancer did not encounter a lung cancer related specialist within the timeframe of our study. Therefore, it remains paramount that we identify patients who have probable, early stage non-small cell lung cancer, and ensure that they enter the progression of care most likely to lead to appropriate treatment. This group may be particularly resistant to surgery either because of a provider's advice against surgery, because of perceptions of co-morbid illness or because the patient avoids referral due to personal health perceptions, disbelief of diagnosis, or attitudes toward cancer or life. Since nearly all individuals with lung masses receive chest computerized tomography scans (chest CT), data derived from these tests serve as a common identifier of patients who do not engage the appropriate system of care for early stage lung cancer just as laboratory blood glucose measurements identify diabetics. The CT protocol is described in our recent report [13]. We feel that the modification utilized in our initial multi-site study meets the intent and spirit of the common rule governing human subject's protection and actually resulted in a net benefit because we ushered lung cancer patients into care who otherwise would not have had this opportunity. This methodology allowed us to broaden recruitment and overcome referral bias. All study enrollees, whether identified by standard recruitment or the CT strategy will be entered into the lung cancer registry and receive intervention as per their randomization.

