Given the continued late stage of lung cancer presentation, particularly among African-Americans [3], we will continue our multi-pronged recruitment approach to find as many patients with early stage, non-small cell cancer as we possibly can. In addition to the electronic CT search, we will continue to engage specialists who see those patients with lung cancer that are indeed referred. Pulmonologists and thoracic surgeons care for the largest concentration of non-small cell lung cancer patients. We'll focus our physician office recruiting efforts on these specialties. As we did with our first prospective study, we will give participating physicians and their office liaisons a project summary sheet that will include the telephone number and beeper number of the PI and research assistant (RA). We will ask that all patients who have the probable diagnosis of resectable lung cancer be referred. We will advise practices that we are responsible for confirming inclusion criteria and obtaining informed consent. In addition, we will provide participating offices information sheets to give to potential enrollees. These documents will describe the study and contain clear statements emphasizing that patient care would not be compromised should individuals decide against participating. For patients who express interest, the office liaison will record the patient's name and telephone number. We will contact each office on at least a weekly basis to remind the staff of the study and to obtain the information on potential enrollees. We will telephone patients to further explain the study and arrange a meeting to obtain informed consent and proceed with the interview.

Patients with lung cancer represent an extremely small proportion of primary care and resident physician practice panels. However, we will not eliminate these practices from consideration. We will attend primary care staff meetings and residency morning reports on a regular basis to remind these physicians of the study. Traditionally, oncologists have been consulted for patients who have advanced disease. With the growing emphasis on adjuvant chemotherapy for early stage lung cancer, these specialists are much more likely to encounter potential study patients. We will therefore regularly attend thoracic oncology conferences and remind oncology physicians, including radiation oncologists of our study.

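### The office referral request uses an undefined term, resectable, that can be read more narrowly than the stage I/II eligibility criteria, so the before/after comparisons may shift by selection

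*Protocol*

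**What the plan says.** **Referral request.** Protocol section E.2 (Patient Recruitment) says of physician offices: "We will ask that all patients who have the probable diagnosis of resectable lung cancer be referred". Neither document defines *resectable*. The next statement to offices is "We will advise practices that we are responsible for confirming inclusion criteria and obtaining informed consent".

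**Eligibility.** Section E.1 requires that "the patient has received a clinical classification of stage I or II disease", with biopsy proof or a malignancy probability of at least 60%. The one exclusion that concerns fitness for surgery is "absolute contraindications by pulmonary function testing". A patient with only relative contraindications is therefore eligible.

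**Clinic route.** Section E.2 has the research assistant and site investigator screen clinic lists in advance. Clinicians are then approached "to confirm the patient's study eligibility and to obtain permission to approach the patient".

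**Baseline.** Section D takes every stage I or II non-small cell case diagnosed in 2008 and 2009 as the baseline for surgical rates, with no filter for resectability. SAP section 6 contrasts proportions before and after feedback and registry, overall and by race (2a, 2b), and before/after surgery rates for Aim 3.

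**The concern.** The referral request and the eligibility criteria do not use the same rule, and the looser word touches the judgement that the trial studies. Section D plans a checklist to remind providers that "surgical contra-indications are often relative and subjective". Section E.4.D describes co-morbidity being over-read in decisions against surgery for African-American patients. An office that takes *resectable* to mean surgical candidate applies that judgement before the study team sees the patient.

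The patients most exposed are those reachable mainly through offices. At USC, section E.2 says about a third of patients are discussed at conference only after the referring physician has settled therapy. Besides the nodule clinic, the stated remedy is more recruitment at thoracic surgery offices. A patient judged unfit and never sent to a surgeon is unlikely to be found there.

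Patients lost this way would mostly not have had surgery. Leaving them out of the enrolled group but not out of the chart-review baseline raises the later rate without any effect of feedback or registry. Section C recognises the same mechanism when it says that registry surgery rates are too high because refusers and drop-outs without tissue proof are missing. The SAP also allows the study to be terminated at interim looks on significant benefit in surgical rates and disparities.

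**Working it through.** **1. The plan's own figure.** SAP section 7 states 80% power with n = 496 to detect 0.63 to 0.69 in a one-sample test. With two-sided alpha of 0.05:

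power = Φ{[(p1 − p0)√n − 1.960√(p0(1 − p0))] / √(p1(1 − p1))}
= Φ{(0.06 × 22.271 − 1.960 × 0.4828) / 0.4625} = Φ(0.843) = 0.800.

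The same formula gives 80.8% for Black patients (n = 159, 0.55 to 0.66) and 78.9% for White patients (n = 337, 0.66 to 0.73). The stated power is reproduced, and rewording the referral request changes none of it.

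**2. Selection model.** Inputs from SAP section 7 are previous-study surgery rates of 0.55 (Black), 0.66 (White) and 0.63 (overall), treated here as unselected. Two further inputs are assumptions, because the documents do not give them:
- c, the share of eligible patients reachable only through offices, taken as equal for surgical and non-surgical patients and for both races;
- f, the share of would-be non-surgical patients in that group whom offices do not refer.

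Observed rate = p / [1 − c·f·(1 − p)].

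Example with c = 20%, f = 20% (Black) and 10% (White): 0.55 / (1 − 0.04 × 0.45) = 0.560; 0.66 / (1 − 0.02 × 0.34) = 0.665; gap 10.4 points against 11.0.

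**3. Gap in percentage points (11.0 without selection).**

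| Omission, Black / White | c = 20% | c = 50% | c = 100% |
|---|---|---|---|
| 20% / 20% | 10.9 | 10.7 | 10.4 |
| 20% / 10% | 10.4 | 9.5 | 7.9 |
| 50% / 25% | 9.5 | 7.0 | 1.2 |

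Equal omission barely moves the gap. A material narrowing needs omission that differs by race together with a large office-only share.

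**4. Overall rate.** With f = 20% in all patients, 0.63 becomes 0.63 / (1 − 0.04 × 0.37) = 0.639 at c = 20%, 0.654 at c = 50% and 0.680 at c = 100%. For selection alone to turn 0.63 into 0.69, c·f must equal 1 − (0.63 × 0.31)/(0.69 × 0.37) = 23.5% of non-surgical patients, or 0.235 × 0.37 = 8.7% of all eligible patients. At c = 20% that cannot be reached: even f = 100% gives only 0.680.

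**5. Which comparisons are exposed.** Referral comes before allocation, so both randomized arms draw on the same selected pool. The chart review does not pass through office referral, so the before/after contrasts do not share that protection.

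**The case against.** The strongest reply is that this is one loose word inside a recruitment plan built to counter exactly this loss.

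- *Resectable* can be read anatomically, as limited-stage disease. The same paragraph opens with the aim of finding as many early-stage patients as possible. This stands: the defect is an ambiguity, not a stated exclusion of unfit patients.
- Offices are told that the study team confirms the criteria. This stands in part, since the team can do so only for patients who are passed on.
- Section E.2 says specialists refer almost uniformly to the multidisciplinary clinic, where the roster is screened in advance. In Greensboro, providers have agreed to refer before treatment decisions. This limits the loss considerably, although the clinician is still asked to confirm eligibility and permit contact.
- The protocol says of its CT search: "This methodology allowed us to broaden recruitment and overcome referral bias". It names provider advice against surgery among the reasons for pursuing patients outside specialist care. The search is aimed at patients who did not meet a lung cancer specialist, so it is a weaker safeguard for those whom a specialist turned down.
- The previous study used the same summary-sheet approach, so its rates may already carry the same selection. Against that benchmark the bias may partly cancel; the documents do not say how that study's sheet described the patients to refer. This does not help the chart-review comparison.

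A reader might infer that the wording will narrow the racial gap, or that the randomized comparison is biased. The documents support neither. The first needs race-differential omission at rates they do not give. The second fails because selection before allocation does not by itself favour an arm. Whether the alternating recruitment dates in section E.2 could be known to referrers is a separate question.

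**Conclusion.** The mismatch is in the text and worth correcting. Offices are asked for a group described by an undefined term that can be narrower than the eligible group, and the likely omissions are patients turned down on relative grounds.

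The consequence is confined to the before/after comparisons (2a, 2b, Aim 3) against the chart review: a possible rise in the enrolled surgery rate and, only if omission differs by race, some narrowing of the gap. The randomized comparisons (1a, 2c) are not biased by this alone.

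The size is unknown. At 20%/10% omission, the gap of 11.0 points becomes 10.4 with a 20% office-only share and 7.9 if every patient comes only through an office. Equal 20% omission gives 10.4 even in that extreme case. All these figures rest on assumed omission rates and office shares, and on treating the previous-study rates as free of selection. This is a cheap improvement to make, not evidence that Aim 2 would be misleading.

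**What to change.** In section E.2 and the office materials, ask for all patients with known or probable clinical stage I or II non-small cell lung cancer, whether or not surgery is planned or has been advised against, and state that the study team applies the section E.1 criteria. The text of the project summary sheet is not in the documents, so it should be checked for the same term.

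Record the recruitment route for every enrolled patient. For patients whom the study team finds on rosters or by the CT search but does not enrol, log route, race and reason. Patients whom offices never pass on cannot practicably be logged, and the fix does not ask for it.

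Add to the SAP a sensitivity analysis for Aim 2 that reports surgery rates by race and recruitment route.

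The cost is a change of wording, three items in the screening log and one extra table. The downside is a few more referrals that fail the written exclusions. The sample size stays at 496.
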